2.3 Data Processing Principles

2.3.1 Definition of Baseline

In this study, baseline is defined as the results of the last non-missing investigations before the phase 1 operation.

2.3.2 Definition of Study Days

Not applicable.

2.3.3 Definition of End of Study Day

A subject completes the study after completing Visit 6 or Visit 7 specified in the protocol. The study ends when the last subject completes the last visit or withdraws from the study prematurely.

2.3.4 Definition of Analysis Window

The analyses performed over time will be performed based on the visits directly collected among the data and thereby the analysis window is not applicable. Only the results of scheduled visits will be summarized in the form of tabulation, and the contents of unscheduled visits will be listed only.

2.3.5 Handling of Missing Data

For the primary endpoint (presence or absence of adhesions), no imputation will be made for missing data during primary analyses. However, during the sensitivity analysis, the missing primary endpoint will be imputed by the Multiple Imputation (MI) method. When developing MI model, the following baseline variables and the variables for phase 1 operation will be used, including the subject's age, gender, randomized adhesion barrier product used during phase 1

operation, presence or absence of adhesions during phase 1 operation, duration of phase 1 operation, blood loss and incision length, and radiotherapy or chemotherapy used at baseline or not.

The secondary endpoint will be analyzed based on the ITT set. No imputation will be made for missing data. All secondary study endpoints will be analyzed using available data.

2.4 Multiplicity Adjustment

Not applicable.

2.5 Subgroup Analyses

In this study, appropriate subgroup analyses will be performed as needed.

Subgroup analysis of the primary endpoint: neoadjuvant radiotherapy (present/absent), study site.

2.6 Pooling of Study Sites

The data of all sites will be pooled and analyzed together.

3 Statistical analysis

3.1 General Information of Subjects

3.1.1 Subjects Disposition

Screened subjects and screen-failure subjects and the reasons for screen failure will be separately described using the number of cases (percentage). Meanwhile, the disposition of randomized subjects in each treatment group and total will be summarized per site. The ITT, PP, and SS analysis sets will be descriptively summarized using the same method.

For all subjects enrolled, the number and percentage of subjects who complete the trial and those who prematurely withdraw from the study will be separately calculated, wherein completion of trial is defined as: a subject completes the study after completing Visit 6 or Visit 7 specified in the protocol. For subjects who withdraw from the study prematurely, the main reasons for withdrawal are classified as: withdrawal of consent, doctor's judgment, adverse event, subject death, loss to follow-up, termination by health authority, sponsor or investigator, and other reasons. The number and percentage of subjects will be calculated for each of the causality categories above.

Subjects' study completion profile and distribution in the analysis sets will be tabulated.

3.1.2 Protocol Deviations

In order to evaluate whether the protocol is implemented as required, before the database is locked, all protocol deviations will be identified based on the data content and protocol requirements, major protocol deviations and whether or not they are included in the PP analysis set will be summarized and described per type, and the number and percentage of subjects with protocol deviation will be calculated. All the major protocol deviations will be tabulated.

3.1.3 Demographics and Baseline Characteristics

The demographics and baseline characteristics will be described per treatment group and in total using the ITT analysis set. The categorical variables, including the gender (male, female), ethnicity (Asian, others), nation (Han, others), preoperative neoadjuvant chemotherapy (yes, no), etc., will be summarized using the missing value, number of cases, and percentage. The continuous variables, including the age, body height, and body weight, etc., will be summarized using the number of cases, missing value, mean, standard deviation, median, quartiles, maximum, and minimum.

For categorical variables, the missing values will not be included in the denominator for percent calculation.

3.1.4 Medical History

The medical history includes the pre-existing conditions and surgical history (including the surgical history within 14 days prior to phase 1 operation, from phase 1 operation to before phase 2 operation, and from end of phase 2 operation to 6-7 months after phase 1 operation). This analysis will be based on the SS analysis set, the pre-existing conditions and surgical history will be coded per treatment group and overall profile using the MedDRA 23.1 coding dictionary. And the medical history will be summarized per System Organ Class (SOC) and Preferred Term (PT) using the number of cases (percentage).

In addition, all information related to the medical history will be tabulated.

3.1.5 Prior Medications, Concomitant Medications, and Concomitant Therapies

Prior medication is defined as any drug used before phase 1 operation (i.e., the medication end date occurs before phase 1 operation).

Concomitant medication is defined as any drug that is used after phase 1 operation (i.e., the medication start date occurs after phase 1 operation) or that has been used before phase 1 operation but continues to be used after phase 1 operation.

The prior medications and concomitant medications will be summarized based on the SS analysis set.

Besides, the prior medications and concomitant medications will be coded according to the WHODRUG dictionary (GLOBAL B3 September 1, 2020) and summarize by frequency and percentage according to the therapeutic classification (ATC 2) and chemical classification (ATC 4).

If the concomitant medication start date is partially missing, the information in [Table 3](#) will be used to determine whether the medication is a concomitant medication.

Table 3 Handling of Missing Date

Known information	Missing information	Prior medication or not
[None]	Year, month, day	Yes
Month, day	Year	Yes
Year	Month, day	Yes, if year \geq year of the first hospital admission
Year, month	Day	Yes, if year = year of the first hospital admission, and month \geq month of the first hospital admission
Year, day	Month	Yes, if year \geq year of the first hospital admission

In addition, the details on each subject's prior medications, concomitant medications, preoperative radiotherapy, chemotherapy, and concomitant therapies will be tabulated.

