##### **2) Exclusion Criteria**

- Female patients who are pregnant or lactating at the time of screening;
- Patient with a history of mechanical bowel obstruction, but except the mechanical bowel obstruction caused by the colorectal cancer treated in the Phase I operation;
- Subjects with history of mid and lower abdominal region or pelvic surgery;
- Patients for whom it is known that loop ileostomy closure within 3 to 9 months is not feasible
- Patients with a history of active intra-abdominal infection such as peritonitis or abdominal abscess;
- Patients with a history of intestinal fistulae;
- Patients with a history of endometriosis;
- Intended use of intraoperative lavage/irrigation with any anti-adhesion solutions other than saline (e.g., dextran, heparin, corticosteroids, icodextrin) or an adhesion barrier other than INTERCEED™;

- Use of immune system suppressants deemed by the investigator to interfere with wound healing;
- Impaired immune system function or coagulation disorders deemed by the surgeon to interfere with wound healing;
- Bevacizumab use within 30 days prior to surgery;
- Subjects with any intra-operative findings identified by the surgeon that may preclude conduct of the study procedures;
- Patients with evidence of distant metastasis of the primary colorectal cancer;
- Patients who underwent abdominal radiotherapy before Phase 1 operation;
- Adhesions (Grade 2-3 adhesion[1]) and/or gross contamination (e.g., caused by tumor perforation) present in the abdominal cavity at the Phase 1 operation;
- The rectal carcinoma radical resection (R0 resection) + preventive ileostomy are not performed in Phase 1 operation;
- Expected resection of other organs (e.g., bladder, uterus, etc.) during Phase 1 operation;
- Use of topical haemostatic products, local chemotherapeutic products or other drugs and/or medical device in abdominal/pelvic cavity which may impact the study primary endpoint judged by the investigator;
- Patient is participating in other investigational drug or device study within 30 days or 5 half-lives of an investigational drug;
- A known history of severe multiple drug allergies or known allergy to cellulose or cellulose derived products;
- Any medications, treatments and/or implanted devices (except INTERCEED™) that on investigator's opinion may be adhesiogenic or may potentially affect the observation of postoperative adhesions;

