### **7.2. Study Process**

#### **7.2.1. Study Flowchart**

The list of time and events of trial is as follows:

Item	Visit 1	Visit 2	Visit 3	Visit 4	Visit 5	Visit 6	Visit 7 h
------	---------	---------	---------	---------	---------	---------	----------------------

Time point	Screening/Baseline: performed within 14 days before Phase 1 operation	Randomization: performed during the Phase 1 operation	Phase 1 operation	Post-Op (Phase 1) through Discharge	Phase 2 operation: performed between 3-9 months after Phase 1 operation a	3 days after Phase 2 operation or Discharge	6-7months after Phase 1 operation
Informed consent	X						
Demographic information	X						
Randomizatio n		X					
Inclusion/Excl usion Criteria	X	X					
Urine/blood pregnancy test	X						
Medical/Surgi cal history b	X				X		X
Concomitant therapy c	X		X	X	X	X	
Physical examination d	X			X	X	X	
Concomitant medications e	X		X	X	X	X	
Procedural data f			X		X		
Mechanical ileus				X	X	X	X
SSI				X	X	X	X
Incision dehiscence				X	X	X	X
Delayed wound healing events				X	X	X	X
Adverse event	X		X	X	X	X	X
Defects of study product			X	X	X	X	
Study completion g						X	X

- a. Other information except operative data should be collected from admission to hospital to the day before operation.
- b. The surgical history should be collected carefully in the two visits.
- c. The neoadjuvant radiotherapy information should be collected at Screening/Baseline visit, if any. The radiotherapy information includes dose and site.
- d. Including height, weight and abdominal sign.
- e. Only including the medicine related to adverse events and which is used beyond two weeks. The neoadjuvant/postoperative chemotherapy protocol and period should also be collected.
- f. The information about the procedure time, hemorrhage volume, use of sterile gloves, target incision, application of study product in the study group should be collected at the visits of Phase 1 operation; the image data and the treatment for

adhesion (if any) should be collected in the Phase 2 operation.

- g. If Visit 6 occurs 6-9 months after Phase 1 operation, the study completion would be in Visit 6. If not, the study completion would be in Visit 7.
- h. Phone contact. If Visit 6 occurs 3-6 months after Phase 1 operation, the Visit 7 need to be conducted.

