### **Postoperative Care:**

Postoperative care will be performed per institutional requirements for clinical practice or specific guidelines regarding postoperative care. Patient status is monitored closely until discharge. Changes in concomitant medications including analgesics will be recorded throughout inpatient stay.

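### SAP Table 3, the rule for incomplete medication start dates, contradicts the SAP's own definitions of prior and concomitant medication, and those definitions leave operation-day-only drugs unclassified

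*SAP*

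**What the plan says.** SAP section 3.1.5 gives two definitions, both anchored on the Phase 1 operation.

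- Prior: "Prior medication is defined as any drug used before phase 1 operation (i.e., the medication end date occurs before phase 1 operation").
- Concomitant: either "the medication start date occurs after phase 1 operation", or the drug was in use before the operation and continues after it.

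For start dates that are partly or wholly missing, the section refers to Table 3, which "will be used to determine whether the medication is a concomitant medication". The answer column of that table is headed "Prior medication or not". Its rows are:

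- nothing known, or only the year missing: Yes;
- year only, or year and day: Yes if the year is the year of first hospital admission or later;
- year and month: "Yes, if year = year of the first hospital admission, and month" is the admission month or later.

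On collection, footnote e to the flowchart in Protocol section 7.2.1 limits concomitant medications: "Only including the medicine related to adverse events and which is used beyond two weeks", plus chemotherapy details. The Visit 3 list repeats the limit, and the SAP's flow chart repeats the footnote. Protocol section 7.2.3, under Postoperative Care, says: "Changes in concomitant medications including analgesics will be recorded throughout inpatient stay".

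**The concern.** Table 3 is a derivation rule that a programmer will code as written. Its stated purpose and its column heading name opposite classes. Its rows test the start date against hospital admission, while the definitions use the operation and, for prior medication, the end date. Two rows with the same aim use different comparisons for the year.

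At stake is whether the prior and concomitant medication tables agree with the definitions printed above them. A record can be filed in the wrong table, or, for use on the operation day only, in neither.

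**Working it through.** The plan gives no figure to reproduce. The check applies the definitions and the Table 3 rows, exactly as written, to example drugs. The dates are assumed for illustration: admission 10 December 2018, Phase 1 on 14 December 2018. The last three columns give Table 3's answer according to which parts of the start date are known.

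| Drug (true start to end) | Class by definition | Nothing, or month and day | Year, or year and day | Year and month |
|---|---|---|---|---|
| A: 15 Dec to 31 Dec 2018 | concomitant | Yes | Yes | Yes |
| B: 3 Jan to 30 Jan 2019 | concomitant | Yes | Yes | No |
| C: 1 Jun 2018 to 1 Mar 2019 | concomitant | Yes | Yes | No |
| D: 1 Jun 2017 to 1 Mar 2019 | concomitant | Yes | No | No |
| E: 1 Oct to 20 Oct 2018 | prior | Yes | Yes | No |
| F: 14 Dec 2018 only | neither | Yes | Yes | Yes |

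**(a) Heading.** Drug A starts the day after surgery. Under the printed heading it is prior for every pattern of missing date, although it did not end before Phase 1.

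**(b) Day-missing row.** Now read the heading as concomitant. Drug B is accepted when only the year 2019 is known, because 2019 is later than 2018. It is rejected when January 2019 is known, because 2019 does not equal 2018. Knowing more about the date turns a correct answer into a wrong one. The case is not remote: the protocol plans nine months of follow-up, so follow-up often crosses into the next year.

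**(c) Continuing drugs.** Drugs C and D were in use before Phase 1 and continued after it, so the second limb of the definition makes them concomitant. The day-missing row rejects both. The other two known-year rows reject D, which began in an earlier year. No row looks at the end date. The converse also occurs: E ended before Phase 1, yet four of the five patterns answer Yes when read as concomitant.

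**(d) Operation day.** This arises even with complete dates. Drug F did not end before 14 December, did not start after it, and was not in use before and after it. It satisfies neither definition. At date level the same gap takes in a drug started that day and continued, and one started earlier and stopped that day.

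**Collection rule.** Footnote e can be read as requiring both conditions or either. Under both readings, a short analgesic change unrelated to an adverse event is not collected. Section 7.2.3 says such inpatient changes are recorded.

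**The case against.** The strongest reply is that this is a heading slip. The sentence above the table names its purpose, the rows read like concomitant rules, and a careful programmer would raise a query. That is probably how (a) arose, but (b) and (c) remain after the heading is corrected.

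On (c), the continuation limb needs no start date, and nothing says Table 3 overrides it when continuation is known. That is fair: the failure arises if the table is applied alone. The SAP states no order of precedence, so it should.

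On (d), clock times could place a drug first given after surgery on the same day as after the operation. This stands, but the definitions are worded in dates. On collection, section 7.2.3 may mean the medical record and footnote e the case report form. That is possible, but the text does not say so.

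Two stronger readings are tempting, and the documents do not support either.

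- A reader might infer that an agent placed in the abdomen during Phase 1 leaves no trace, so that control-arm contamination is hidden and the per-protocol set cannot remove it. The exclusion criteria do name "Use of topical haemostatic products, local chemotherapeutic products or other drugs and/or medical device in abdominal/pelvic cavity" as a concern where it may affect the primary endpoint. But concomitant therapy is a separate Visit 3 item under footnote c, not e. Protocol section 7.1.5 makes any intervention that the investigator judges may affect adhesion formation at the target incision a withdrawal ground. Protocol sections 8.9 and 14 and SAP section 3.1.2 require deviations to be reported and those that are major to be settled before database lock. These routes rest partly on judgement, but they exist, and nothing in the documents shows that such use occurred.
- A reader might take the share of follow-up falling in the next calendar year as the misclassification rate. That share is calendar time. It bears only on post-operative starts with the day missing, and depends on when drugs are started, which the documents do not give.

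**Conclusion.** Table 3 is wrong as written in respects (a) to (c), and the two definitions leave gap (d). Points (a) to (c) apply only to records with a partly or wholly missing start date; complete dates follow the definitions. Point (c) assumes the table is applied without the continuation limb, and (d) assumes date-level data. The collection texts conflict on their face and must be reconciled.

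The consequence is limited to the descriptive medication tables and listings. Prior or concomitant class does not enter the primary comparison (SAP section 3.3.1), the multiple-imputation model (section 2.3.5, which uses baseline radiotherapy or chemotherapy) or the conditional-power calculation (section 4). The documents give neither the number of incomplete dates nor their pattern, so the number of affected records cannot be estimated. The correction is still worth making because the rules are explicit and produce wrong tables if followed.

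**What to change.** In SAP section 3.1.5:

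1. Head the Table 3 answer column *Concomitant medication or not*.
2. Replace first hospital admission by the Phase 1 date, and compare year and month jointly, so that a later year is always Yes.
3. Let the end date decide: a drug is concomitant unless the known parts of its end date place it before Phase 1. A start before Phase 1 then never produces a No on its own. This settles drugs C, D and E.
4. Define concomitant as starting on or after Phase 1, or in use before and not ended before it. Every operation-day pattern under (d) then has a class.

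Separately, reconcile footnote e of Protocol section 7.2.1 and the Visit 3 list with the Postoperative Care text in section 7.2.3, and state which medications go into the case report form.

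The SAP cost is a few lines of text and one reprogrammed derivation, with a rerun of any medication tables already produced. The SAP changes need no new data and do not alter any efficacy analysis.

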3.2 Surgical Data and Product Use Profile

3.2.1 Surgical Data

The surgical data of phase 1 operation will be descriptively summarized based on the SS analysis set.

The variables, including whether or not adhesions are observed during operation (yes, no), site of adhesions (four abdominal quadrants), extent and severity (Grades 1, 2, 3) of adhesions, whether the adhesions are treated or not (yes, no), and closure of target incision (use of absorbable suture to suture the target incision, others), will be summarized using the number of cases (percentage). Other variables, including the duration of operation, blood loss, number of sterile gloves used, length of target incision, etc., will be summarized using the number of cases, mean, standard deviation, median, quartiles, maximum, and minimum.

3.2.2 Product Use

The product use profile in the experimental group will be tabulated based on the SS analysis set.

3.3 Effectiveness Endpoints Analysis

3.3.1 Primary Effectiveness Endpoint Analysis

The primary effectiveness endpoint is the proportion of subjects free of incision adhesions at the main target incision site observed in the two groups (experimental group and control group). The ITT and PP analysis sets will be used to analyze the primary effectiveness endpoint. The ITT analysis will be regarded as the primary analysis, and PP analysis as supportive analysis.

The statistical hypotheses for the primary endpoint are as follows:

- $H_0: P_I \leq P_C$
- $H_a: P_I > P_C$

Where P_I is the proportion of subjects free of adhesions in the experimental group, and P_C is the proportion of subjects free of adhesions in the control group.

The proportion of subjects free of adhesions in each treatment group will be summarized and calculated as: number of subjects free of adhesions divided by the total number of subjects randomized to receive the treatment. The two-sided 95% confidence interval for the proportion of subjects free of adhesions in the treatment groups will be provided by the Clopper-Pearson method. In addition, the two-sided Wald 95% confidence interval for the difference of two independent proportions (experimental group minus control group) will be constructed and used to test the null hypothesis for the superiority. If the lower limit of the confidence interval is greater than 0, it can be concluded that the experimental group is superior to the control group.

```
proc freq data =data;
  weight count;
  tables group*outcome / riskdiff(CL=WALD);
run;
```

Furthermore, a sensitivity analysis for the primary endpoint will be added. The stratification factor “presence or absence of neoadjuvant radiotherapy” will be adjusted to estimate the rate difference of the two groups and corresponding 95% CI.

3.3.2 Secondary Effectiveness Endpoint Analysis

The secondary effectiveness endpoints will be summarized based on the SS analysis set.

The incidence of mechanical ileus in subjects will be descriptively summarized per treatment group using the number of cases (percentage). The incidence of ileus will be compared between groups using the chi-square test, with the P-value calculated. The two-sided 95% confidence interval for the proportion of subjects with mechanical ileus in the treatment groups will be provided by the Clopper-Pearson method. In addition, the two-sided Wald 95% confidence interval for the difference of two independent proportions (experimental group minus control group) will be constructed.

The extent (no adhesions, grades 1, 2, 3) and severity (no adhesions, grades 1, 2, 3) of adhesions at the target surgical incision site and four abdominal quadrants observed during the phase 2 operation will be descriptively summarized per treatment group using the number of cases (percentage).

In addition, the extent and severity of adhesions at the target incision will be compared between groups using MH (Mantel - Haenszel) chi-square test, with the P-value calculated.

```
proc freq data=data;  
  tables treat*response / chisq cmh nocol nopct;  
  weight count;  
run;
```

